Thus, effective cessation programs for light smokers need to incorporate traditional cognitive strategies that promote self-regulation, behavioral learning strategies to optimize the ability to unlearn smoking cues, and elements to increase motivation, decrease barriers, increase self-efficacy and improve outcome expectations.

In this small, randomized controlled pilot trial, we will test the feasibility, acceptability, and preliminary efficacy of a combination of cognitive behavioral cessation counseling and cue exposure treatment, a cue driven treatment that has been found effective in the treatment of substance use. Further, we will extend cue exposure therapy beyond the clinic or laboratory by using interactive texting to help light smokers transfer their newly learned cue extinction skills into their natural environment. Interactive

texting will include both self-monitoring and extinction of cue extinction skills. Interactive texting for real-time data collection will include participants taking photographs of cues they identify as salient and triggering of their desire to smoke as well as texting when they smoke and their craving levels. We will incorporate the participants own photographs into their tailored cue exposure treatment conducted in the clinic

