### **DESIGN & PROCEDURES**

#### ***Design***

The two-arm trial compares Arm 1) standard smoking cessation counseling and 2) enhanced cue exposure treatment. For all arms, we will conduct a phone screening, provide smoking cessation counseling, and an in-person follow-up visit. The primary outcome will be feasibility and acceptability. The secondary outcome will be biochemically-validated cessation 1-week post-intervention.

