## **STUDY INTERVENTIONS**

### ***Randomization***

We will randomize participants into one of two arms: Arm 1) standard smoking cessation counseling and 2) enhanced cue exposure treatment. The randomization will be automated and drawn from a random number generated list programmed onto the laptops. We will stratify randomization on the number of cigarettes per day and native /converted smoking status.

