### **DATA ANALYSIS & STATISTICAL CONSIDERATIONS**

The purpose of this study is to evaluate the feasibility, acceptability, and preliminary efficacy of an intervention to promote smoking cessation among light smokers. The intervention arms will be compared using descriptive statistics. Results from these analyses will be used to prepare a P01 grant application.

**Statistical Analysis of Feasibility Aim 1:** For this feasibility aim, the two arms will be combined. We have two feasibility metrics. We will consider the intervention feasible if we enroll 6 light smokers per month and 75% complete at least 2 study visits.

**Statistical Analysis of Aim 2:** For this acceptability aim, we will ask participants in all arms how useful the intervention was (1="Not at all useful" to 5="Extremely useful"), whether the intervention will change their smoking (1="Will not change at all" to 5="Will change a lot"), and whether they would recommend the program to a friend (1="Definitely would not recommend" to 5="Definitely would recommend"). For the intervention to be deemed acceptable, 75% of participants in Arm 2 would have to rate each item a "4" or a "5." Note that this decision rule has nothing to do with the efficacy of the control arm. The percentage of participants endorsing "1", "2", "3", "4", and "5" on each of the three Likert-scaled items will be calculated and compared between arms. This comparison will be used to detect any unexpected, gross difference between arms. For example, if arm median on "how useful was the intervention?" were "2" and "5", this result would be considered both unexpected and noteworthy regardless of which arm did better.

**Statistical Analysis of Aims 3 and 4:** This aim will compare the arms on the efficacy of the intervention. We'll start by calculating an estimated prevalence (with 95% confidence interval) for the binary measure of point prevalence, with the confidence interval based on the standard formula for the standard error

or a binomial proportion. We're interested in all 3 pairwise comparisons between the groups, recognizing that only the comparison between groups 1 and 2 is randomized. Each of the comparisons would be based on a chi-square or Fisher's exact test as appropriate. Because this is a pilot study, which is not intended to be a definitive assessment of efficacy all 3 comparisons, we would use a cut-off value of  $p=0.05$  for declaring statistical significance.

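### Randomisation is stratified on two factors but the planned Arm 1 v Arm 2 abstinence test ignores the strata; if the strata are balanced and prognostic, some power is lost

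*Combined protocol and SAP*

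**What the plan says.** On allocation, the Randomization section states: "We will stratify randomization on the number of cigarettes per day and native /converted smoking status". The assignment is "drawn from a random number generated list programmed onto the laptops". It gives no cut-points for cigarettes per day, no blocks and no other device to balance the arms within strata.

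On analysis, the text for Aims 3 and 4 starts by "calculating an estimated prevalence (with 95% confidence interval) for the binary measure of point prevalence", and then: "Each of the comparisons would be based on a chi-square or Fisher's exact test as appropriate". Significance is declared at p=0.05; sidedness is not stated. There is no interval for the difference between arms, and neither stratification factor enters any test or estimate. The text speaks of three pairwise comparisons but recognises that only group 1 v group 2 is randomised, so the strata bear on that one.

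On the status of the result, the plan describes it as "not intended to be a definitive assessment of efficacy", and the trial as small, with no sample size.

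**The concern.** Stratified randomisation is normally used to make the arms alike on factors thought to matter. When it succeeds, differences between strata no longer contribute to chance variation in the treatment comparison. A crude chi-square or Fisher test does not know this. Its variance still contains the between-stratum part, so it can reject less often than 5% under the null and miss some real effects.

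What is at stake is a few points of power, and a correctly stated standard error, in a comparison that has a formal significance cut-off and feeds a grant application. The design has already collected the stratum for each participant, and the plan gives no reason for leaving it out.

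**Working it through.** The plan states no sample size, power, quit rate or effect size, so it has no figure to reproduce. Documented inputs are the two factors, the random-number list, the crude test, alpha 0.05 and the eligibility range of 1 to 10 cigarettes per day. **Everything else below is assumed:** two-sided 0.05, 1:1 allocation, two levels per factor giving four equally likely strata, a common odds ratio of 4 for power, and the control abstinence rates shown.

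**Step 1. Size of the crude test under exact within-stratum balance.** Let W be the mean of p(1-p) over strata and T = P(1-P), with P the mean rate. Then size = 2 x [1 - Phi(1.96 / sqrt(W/T))].

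| Control rates by stratum | W | T | W/T | Size |
|---|---|---|---|---|
| 15% in all | 0.1275 | 0.1275 | 1.000 | 5.0% |
| 8/12/17/25% | 0.1270 | 0.1310 | 0.969 | 4.6% |
| 10/10/30/30% | 0.1500 | 0.1600 | 0.938 | 4.3% |
| 5/15/25/45% | 0.1525 | 0.1744 | 0.875 | 3.6% |
| 3/8/20/40% | 0.1257 | 0.1460 | 0.861 | 3.5% |

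For example, for 10/10/30/30%: W = (0.09 + 0.21)/2 = 0.15, T = 0.20 x 0.80 = 0.16, and 1.96/sqrt(0.9375) = 2.024.

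**Step 2. Power with balance enforced.** Simulated crude chi-square against Cochran-Mantel-Haenszel (CMH) without continuity correction.

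With exact balance:
- 5/15/25/45%, 20 per arm: 39.3% to 45.1% (+5.8); size 3.7% v 4.9%.
- 5/15/25/45%, 40 per arm: 69.4% to 75.8% (+6.4); size 3.8% v 5.0%.
- 10/10/30/30%: +2.2 points (20 per arm), +3.3 (40 per arm).
- Non-prognostic strata: -1.1 and +0.3 points.

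With blocks of 4 and stratum sizes left to chance:
- 15% in all: 47.4% to 45.3% (-2.1) at N=40; 63.6% to 63.3% (-0.3) at N=60.
- 8/12/17/25%: 44.4% to 44.1% (-0.3) at N=40; 59.7% to 61.2% (+1.5) at N=60.
- 3/8/20/40%: 33.0% to 38.8% (+5.8) at N=40; 47.9% to 56.0% (+8.1) at N=60.

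**Step 3. Simple randomisation within strata.** The documents do not rule this out. With 3/8/20/40%, crude chi-square size is then 5.2%, 4.9% and 5.4% at N=40, 60 and 100, so it is not conservative. Against crude chi-square, CMH gains 1.6 points (20 per arm) and 5.1 (40 per arm) with 5/15/25/45%. It loses 1.3 with 10/10/30/30% at 20 per arm, and 4.1 and 2.0 with non-prognostic strata at 20 and 40 per arm. Across runs with weak or non-prognostic strata, the change ran from about -5 to +4 points.

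**Step 4. Precision of the risk difference.** With blocks of 4, N=40 and 3/8/20/40%, the true standard deviation of the estimate is 0.112 crude and 0.112 stratified. The crude model-based standard error averages 0.120, and 0.120/0.112 = 1.07. The estimate itself hardly changes; its crude standard error is about 7% too large.

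**Step 5. Which stratified test.** Power of a chi-square/Fisher rule (Fisher if any expected count is below 5) against exact stratified CMH, blocks of 4:
- N=40: 45.3% to 38.8% non-prognostic; 43.8% to 39.1% with 10/10/30/30%; 38.8% to 37.9% with 5/15/25/45%.
- N=80: 77.2% to 72.5% non-prognostic; 71.2% to 72.0% with 5/15/25/45%.

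Uncorrected asymptotic CMH reaches 45.1% and 76.4% in the two 5/15/25/45% cases. It kept its size at or below about 5%, and its worst result against the chi-square/Fisher rule was about -2 points.

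**The case against.** The strongest case on the other side has four parts.

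- **The mechanism is conditional.** It needs enforced balance and prognostic strata. The protocol mentions only a random-number list, gives no quit rates by stratum, and narrows cigarettes per day to 1 to 10. The Background describes native and converted smokers as subgroups but does not say that they quit at different rates. This stands, and it is why the loss is stated as a range.
- **Stratifying can cost power.** With few participants, strata become uninformative: at N=20, CMH is undefined in 3 to 4% of null trials. The exact version often loses to the planned rule. This also stands, and it decides the form of the fix.
- **A test below its nominal level is still valid.** True. Fisher's test is in any case conservative at these sizes whatever the strata (2.2% at N=40 and 3.0% at N=60 with no prognostic effect).
- **The comparison is preliminary.** The section opens with "The intervention arms will be compared using descriptive statistics", and the Design section says "The secondary outcome will be biochemically-validated cessation 1-week post-intervention". This limits the weight of the point but does not remove it: the plan still tests at p=0.05, and the Data Collection Methods section calls abstinence the primary outcome.

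A reader might infer that ignoring the strata makes this test conservative and gives away power and precision at no cost. The documents do not support that. Without enforced balance the crude chi-square holds its level, non-prognostic strata can make stratifying costly, and with blocking the estimate is no more variable when crude. Nor can the plan be faulted for too wide an interval for the difference, because it contains none.

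**Conclusion.** The mismatch is real: two factors govern allocation, and neither enters the analysis of the randomised comparison. Its consequence is conditional and modest.

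Under balanced allocation and the assumed inputs (four strata, odds ratio 4), the change in power over crude chi-square is about -1 to 0 points with non-prognostic strata, +2 to +4 with weak strata (10/10/30/30%) and +6 with strong ones, for 40 to 80 participants. Leaving stratum sizes to chance, and using other assumed rates, widens this to about -2 and +8. If balance is not enforced and the strata are sparse and not prognostic, the stratified test can lose up to about 5 points.

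Sample size, stratum levels, quit rates and effect size are all assumptions, so no particular loss can be attributed to this trial. The change is still worth making: it is cheap, the uncorrected stratified test is nearly always level with or better than the planned chi-square/Fisher rule, and the accompanying risk difference supplies an interval that the plan lacks.

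**What to change.** In the analysis text for Aims 3 and 4, for Arm 1 v Arm 2 only:

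- Test abstinence with a CMH test without continuity correction, stratified by the randomisation strata.
- Report the Mantel-Haenszel risk difference with its 95% CI, with the crude percentages by arm alongside.
- State in advance that strata collapse to native/converted status if any stratum holds only one arm. This depends on allocation alone, so it can be applied without sight of outcomes.
- Do not default to the exact stratified test, which can cost power in sparse data.

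In the Randomization section, state the cigarettes-per-day levels and how allocation is made within strata; until then the strata are not defined.

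The cost is a few sentences in two sections and no new data, since both factors must be known at randomisation. The downside to accept is the possible small power loss given in the verdict.

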## **DATA & SAFETY MONITORING**

The quality of data collection will be enhanced through extensive training of all personnel involved in data collection. Quality control checks will include feedback on protocol fidelity, interpersonal skills, and data entry and cleaning.

We will monitor participant safety by maintaining ongoing contact with staff and convening weekly meetings between the investigators and the project team. The study field staff will be trained and provided with a written protocol that instructs them to contact the Project Coordinator if any reportable AE occurs. The Project Coordinator will follow-up with participants within 48 hours to ensure that the event has been resolved and document actions. All non-reportable AEs will be reported to the Principal investigator at regular meetings and the IRB via annual reports.

## **PRIVACY, DATA STORAGE & CONFIDENTIALITY**

Prior to any physical screening procedures, we will inform participants in their consent forms of the data storage and confidentiality safeguards, which are practiced according to current HIPAA regulations. Study records that identify participants will be kept confidential as required by law. Blood and urine specimens will be sent to LabCorp for processing. Name, date of birth, and gender will be included with each specimen. Except when required by law, participants will not be identified by name, social security number, address, telephone number, or any other direct personal identifier in study records disclosed outside of Duke University Health System (DUHS) (except to LabCorp). For records disclosed outside of DUHS, participants will be assigned a unique code number. The key to the code will be kept in a locked file in the PI's office separate from the locked file where the study records are stored.

People Designs, a Durham-based consulting and development firm, will manage the texting system. Texting data will be housed on a web-accessible interface behind the Duke firewall so that study staff can access the participant texts and data is stored securely. Only People Designs staff listed on the Outside Key Personnel list will have access to the system and text-based data.

Data will be collected by staff both in person and on the telephone. All participants will be assigned a code number that is the sole identifier on all study data forms. Survey data will be collected on paper-and-pencil surveys and entered into computers via a password protected REDCap form on a secure network server. Participants may also complete the surveys directly into REDCap. Study staff may enter data directly into REDCap during the interviewer-administered surveys. Access will only be granted to study staff who need to access the data. Staff will store active participant files in personal locking file cabinets. Access to this file will be limited to study personnel.

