### Follow-up

For the final visit, participants from all arms will return to the Tobacco Cessation Lab to complete the follow-up assessment. This will occur one week after Visit 5 and one week after Visit 4, respectively. They will complete a questionnaire and we will assess abstinence via 7-day point prevalence.

Participants will provide a saliva sample to biochemically validate their smoking status based on their cotinine levels. At the follow-up visits, we will ask participants if we can contact them after to ask for feedback on the pilot study. If they agree, we will call them or meet them in person to ask for their input.

Participants may also be asked at the time of visits to be audio-recorded for data or quality assurance purposes. They can refuse to be audio-recorded and can still participate in the study.

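### The plan lets study staff take the primary acceptability ratings by interview, although self-completion is already available and would better protect them

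*Combined protocol and SAP*

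**What the plan says.** **Survey modes.** The section headed PRIVACY, DATA STORAGE & CONFIDENTIALITY gives three routes:

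- Paper comes first: "Survey data will be collected on paper-and-pencil surveys and entered into computers via a password protected REDCap form on a secure network server".
- Direct entry by the participant: "Participants may also complete the surveys directly into REDCap".
- Interview: "Study staff may enter data directly into REDCap during the interviewer-administered surveys".

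The same section adds: "Data will be collected by staff both in person and on the telephone".

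**Follow-up.** The Follow-up section says: "They will complete a questionnaire and we will assess abstinence via 7-day point prevalence". It does not say who fills in the questionnaire.

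**Acceptability.** The Design section states: "The primary outcome will be feasibility and acceptability". Under Aim 2 in the statistical section, participants rate from 1 to 5 "how useful the intervention was", whether it will change their smoking, and whether they would recommend it. The intervention counts as acceptable only if 75% of Arm 2 give a 4 or 5 on each of the three items.

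**Abstinence.** The Design section names biochemically validated cessation as the secondary outcome. The Specific Aims list self-reported 7-day abstinence as part (a) of Aim 3 and validated cessation as part (b). The efficacy analysis names only point prevalence. The Data Collection Methods section calls abstinence the primary outcome, which does not match the Design section. I follow the Design section here, and on either reading saliva validation is attached to abstinence.

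**Staff.** Study staff counsel both arms and run the cue exposure sessions. No independent or masked assessor is described.

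**The concern.** People asked face to face, or by telephone, to rate a programme by someone from the team that delivered it may answer more kindly than they would in private. That is a methodological judgement, and the documents give no figure for it.

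The acceptability items are the most exposed outcome in this trial. They are subjective and nothing can verify them. They are judged against a fixed percentage in one arm, so no subtraction between arms can cancel an upward shift. The results are meant to support a grant application, so a pass owed partly to politeness would carry forward.

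The plan does not ask for the mode of each response to be recorded. If interviews were used for some participants, the analysis could not show whether they mattered.

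**Working it through.** The plan gives no sample size and no expected acceptability rate, so there is no figure of its own to reproduce. The check has two parts.

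**1. Does any section fix the mode for these items?**

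| Section | What it settles |
|---|---|
| Privacy and data storage | Permits paper, participant entry and interview; does not link any of them to particular items |
| Follow-up | A questionnaire is completed; self-completion or interview not stated |
| Data Collection Methods | Follow-up surveys include process questions; mode not stated |
| Aim 2 analysis | Participants are asked the three items; mode not stated |

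Interview is therefore permitted for these items and nowhere excluded.

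**2. How sensitive is the 75% rule to an upward shift?**

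Inputs: the 75% threshold is from the Aim 2 analysis. The number of Arm 2 raters (n) and the share giving a 4 or 5 (p) are my assumptions.

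Formula for one item: P(pass) = P(X ≥ r), with X ~ Binomial(n, p) and r = 0.75n rounded up.

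| n | r | p = 0.65 | p = 0.70 | p = 0.75 |
|---|---|---|---|---|
| 10 | 8 | 0.262 | 0.383 | 0.526 |
| 15 | 12 | 0.173 | 0.297 | 0.461 |
| 20 | 15 | 0.245 | 0.416 | 0.617 |
| 30 | 23 | 0.124 | 0.281 | 0.514 |
| 40 | 30 | 0.121 | 0.309 | 0.584 |

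With n = 20, a shift from 65% to 75% takes the chance of passing from 25% to 62%. Over n = 10 to 40 it goes from 12–26% to 46–62%. That is a ratio of 0.526/0.262 = 2.0 at the least and 0.584/0.121 = 4.8 at the most.

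**From one item to the rule.** All three items must pass, so the chance for the whole rule cannot exceed the one-item chance. With n = 20 and the same p for each item:

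- if the items agree perfectly, the chance goes from 25% to 62%;
- if they are independent, it goes from 0.245³ = 0.015 to 0.617³ = 0.235, or about 1.5% to 23%.

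**Dilution.** Only interviewed participants would be affected. If a proportion f is interviewed and interview adds d points, the average shift is f × d. With f = 0.5 and d = 10, the shift is 5 points. Starting from 65%, the one-item chance at n = 20 then goes from 0.245 to 0.416.

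**The case against.** The strongest reply is that interview is an option and not the plan. Paper is listed first, and completing a questionnaire reads most naturally as self-completion. The references to interview and telephone stand in a section about data storage and could refer to the telephone screening or the optional feedback call after follow-up. This is fair, and it limits how often the problem would arise. It does not remove the problem, because the permission covers surveys in general and no section exempts these items.

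Four stronger readings are tempting and are not supported:

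- *The person who treated a participant will collect that participant's ratings.* The documents show the same role, not the same individual, and do not say that the ratings will be taken by interview.
- *Abstinence results are inflated.* Saliva is collected at follow-up, and the secondary outcome in the Design section is validated cessation. What remains exposed is self-reported Aim 3(a) and the efficacy analysis, which names only point prevalence.
- *The bias falls mainly on Arm 2, or mode differs by arm.* Arm 2 has five counselling or treatment visits (Visits 1 to 5), and counselling in Arm 1 ends at Visit 3. However, the same survey options apply to everyone, staff counsel both arms, and nothing shows that more contact yields kinder answers. The comparison of ratings between arms looks only for gross differences, which a shift of 5 to 10 points would hardly create.
- *The calculation measures interview bias.* It shows how steeply the rule responds to the share of favourable ratings. It does not show how far interviewing moves that share, or how much self-completion would recover.

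**Conclusion.** The concern holds in a limited form. A primary, subjective outcome with a fixed pass mark may be collected by interview by the role that delivers the programme, and the plan neither excludes this nor asks for the mode to be recorded. The likely direction of any effect is upward; its size is unknown. The illustrated rise from 25% to 62% rests on an assumed 20 raters and an assumed average shift of 10 points, and it covers one item. It is an upper limit for the three-item rule at those values, and partial use of interviews would shrink it. For abstinence the point is secondary. This is a worthwhile improvement to data collection, not a contradiction or an error of analysis in the plan.

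**What to change.** Add a short statement to the data collection section. In both arms, the three acceptability items and the follow-up 7-day abstinence question are self-completed in REDCap, on site or by remote link, or on paper that the participant seals, out of view of staff. Record the mode of each response, and flag any interviewer-assisted or telephone response. Interviews can stay in use for other survey sections.

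The cost is small. Participant entry and paper forms are already allowed, and ability to read English is an eligibility criterion, so few people should need help. The remote link covers participants who miss the follow-up visit. The telephone route need not be closed, so responses are not lost for the sake of the rule. The downside is that a few assisted or telephone responses must be flagged and may need a sensitivity check, in which the Arm 2 percentages are recalculated without them.
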